8.2.2. Biochemical parameters

Biochemical parameters for safety and inflammatory outcomes are detailed in the SoA (section 1.2) and Appendix 2. In addition, plasma, serum and full blood samples will be biobanked (level II and III) for analysis of SARS-CoV-2 antibodies and exploratory markers as detailed in section 8.4.

8.2.3. Patient reported outcome measures (PROMs)

The Oslo COVID-19 Quality of Life Questionnaire Provisional Weekly 80 item version (The Oslo COVID-19 QLQ-PW80 ®) will be used to collect the patient's reported outcome (PRO) at Day 91. The responses will be collected using a web-based form.

This COVID-19 specific questionnaire has been developed since March 2020 according to international guidelines⁴ based on literature review, and interviews with health care professionals and patients in seven countries. It covers the perspectives of patients with COVID-19 disease related to their symptoms, functioning, concerns and general health status.

Most items have a 4-point verbal rating scale (not at all, a little, quite a bit and very much), while items 79 and 80, have a 7-point modified visual analogue rating scale (ranging from very poor to excellent). The recall timeframe is 7 days, and it takes 15-20 minutes to fill in the questionnaire. A daily version is available. This provisional version of the questionnaire will be psychometrically tested in an international validation study (NCT04740372) involving more than 10 countries, and the scoring manual and description of subscales will be available in spring 2021.

All patients will be asked to fill in the questionnaire at Day 91 (\pm 14 days). In addition, institutions on level III may be asked to participate in an extended PROM-protocol, involving assessments at day 1 and at discharge. Health care professionals may read the questions for the patient, but the patient should respond themselves.

8.3. Safety Assessments

8.3.1. Physical examination

Physical examination will be performed according to local procedures. Any new findings will be recorded as medical history if found before randomization or as adverse events if discovered after randomization.

8.3.2. Vital signs

Vital signs collection will be performed according to local procedures

- Body temperature (°C)
- Pulse rate (beats/min), regular/not regular
- Blood pressure (mmHg), diastolic and systolic pressure
- Respiratory rate (breath/min)
- Oxygen saturation (%)

8.3.3. Electrocardiograms

Electrocardiograms (ECGs) will be performed according to local procedures. If registered, the following will be registered from ECG machine reading:

- Heart rate
- PR
- QRS
- QT
- QTc

8.3.4. Other clinical assessments

The use of vasopressors, dialysis, continuous renal replacement therapy, prone positioning (hours/day) and exact recording of pO₂- and FiO₂-values will be registered at the assessment timepoints when indicated.

8.3.5. Clinical safety laboratory tests

See SoA table (section 1.2) as well as Appendix 2 for the list of clinical laboratory tests to be performed and the SoA for the timing and frequency.

The investigator must review the laboratory report, document this review, and record any clinically significant changes occurring during the study as an AE. The laboratory reports must be filed with the medical records.

Abnormal laboratory findings associated with the underlying disease are not considered clinically significant unless judged by the investigator to be more severe than expected for the participant's condition. Abnormal laboratory findings associated with adverse events of special interest (AESI) as detailed in the intervention-specific sub-protocols should be considered clinically significant unless judged otherwise by the investigator.

All laboratory tests with values considered clinically significantly abnormal during participation in the study or within five half-lives after the last dose of study intervention should be repeated until the values return to normal or baseline or are no longer considered clinically significant by the investigator or medical monitor.

- If clinically significant values do not return to normal/baseline within a period of time judged reasonable by the investigator, the aetiology should be identified, and the sponsor notified.
- All protocol-required laboratory tests, as defined in Appendix 2, must be conducted in accordance with the laboratory manual and the SoA (section 1.2).
- If laboratory values from non-protocol-specified laboratory tests performed at the institution's local laboratory require a change in participant management or are considered clinically relevant by the investigator (e.g., SAE or AE or dose modification), then the results must be recorded.

8.3.6. Pregnancy testing

Pregnancy test by human chorionic gonadotropin (HCG) levels in blood or urine should be performed at screening or baseline before receiving first dose of investigational medicinal product.

8.3.7. Suicidal ideation and behaviour risk monitoring

Detailed in the intervention-specific sub-protocol if applicable.

8.4. Biomarkers

Biobanking will be performed according to procedures described in Appendix 2 (level II and III), and samples taken at baseline (D1), Day 3, 8, 15 and 22 (all ± 1). Depending on research questions, the following volumes of blood will be obtained, as further detailed in the IMP specific protocol and standard operating procedure (SOP):.

- Serum: 1.5-2 mL (3-4 mL blood)
- EDTA Plasma: 1.5–2 mL (3-4 mL blood)
- Citrate Plasma: 1-2 mL (2-3 mL blood)
- Whole blood: 2 mL

Naso/oropharyngeal swab will be taken at baseline, Day 3, 8 and 15 (all ± 1).

Sponsor may store samples for up to 25 years after the end of the study. Additionally, with participants' consent, samples may be used for further research by sponsor or others such as universities or other companies to contribute to the understanding of SARS-CoV-2 or other diseases, the development of related or new treatments, or research methods.

8.5. Imaging

Details of imaging protocols will be developed for add-on sub-studies (level III).

8.6. Adverse Events (AEs), Serious Adverse Events (SAEs), and Other Safety Reporting

The complete safety data circuit and safety working instructions is available in a standard operating procedure (SOP) related to the EU-SolidAct trial.

The definitions of the EU Directive 2001/20/EC Article 2 based on the principles of GCP and EU guidance ENTR/CT 3 apply to this trial protocol, when required local requirements should also apply.

Table 8.3: Definitions of Adverse Events

TERM	DEFINITION
Adverse Event (AE)	Any untoward medical occurrence in a patient or clinical trial participant, which does not necessarily have a causal relationship with the research procedures or the investigational medicinal product (IMP).
Adverse Reaction (AR)	Any untoward and unintended responses to an IMP related to any dose administered.
Serious Adverse Event or Reaction (SAE/SAR)*	Any AE/AR that, at any dose, results in: 
 - death; - a life-threatening AE; - hospitalization or prolongation of existing hospitalization; - a persistent or significant disability or incapacity; - a congenital anomaly/birth defect; - an "important medical event"
Suspected Unexpected Serious Adverse Reaction (SUSAR)	An unexpected adverse reaction is an AR of which the nature, outcome, frequency or severity is not consistent with the applicable Reference Safety Information (RSI): SmPC or Investigator's Brochure (IB).

New fact**	Any safety data that could modify significantly the evaluation of the benefit/risk ratio of the IMP or the clinical trial, likely to affect the safety of participants or that could modify the IMP administration, the trial documentation or the conduct of the trial, or to suspend, interrupt or modify the protocol or similar trials.
-------------------	---

** EXCEPTIONS: the following events are not considered as SAE requiring immediate reporting to the sponsor:*

- the participant is formally admitted to a hospital for medical reasons with no seriousness criterion and does not require overnight hospitalization*
- elective or previously scheduled surgery or medical treatment;*
- hospitalization for social or administrative reasons;*
- pre-existing diseases or present conditions detected prior to start of study drug administration and which do not worsen.*

***Example: a SAE which could be associated with the trial procedures and which could modify the conduct of the trial, a significant hazard to the subject population such as lack of efficacy of an IMP used for the treatment of a life-threatening disease, recommendations of the data safety monitoring board, if any, where relevant for the safety of participants.*

8.6.1. Time period and frequency for collecting AE and SAE information

- All AEs and SAEs will be collected from the signing of the informed consent form (ICF) until the follow-up visit at the time points specified in the SoA (section 1.2.).
- Except disease-related events as defined in section 8.6.9. and exceptions mentioned above, all SAEs will be recorded and reported to the sponsor and the delegated designee, Inserm-ANRS Pharmacovigilance Office, immediately and under no circumstance should this exceed 24 hours, as indicated in the trial Safety Management Plan (SMP). The investigator will submit any updated SAE data within 24 hours of it being available.
- Investigators are not obligated to actively seek information on AEs or SAEs after conclusion of the study participation. However, if the investigator learns of any SAE, including a death, at any time after a participant has been discharged from the study, and he/she considers the event to be reasonably related to the study intervention or study participation, the investigator must promptly notify the sponsor and the delegated designee, Inserm-ANRS Pharmacovigilance Office.

8.6.2. Method of detecting AEs and SAEs

- Care will be taken not to introduce bias when detecting AEs and/or SAEs. Open-ended and non-leading verbal questioning of the participant is the preferred method to inquire about AE occurrences.

8.6.3. Follow-up of AEs and SAEs

- After the initial AE/SAE report, the investigator is required to proactively follow each participant at subsequent visits/contacts. All SAEs and AEs of special interest (AESI, as defined in section 8.6.11) will be followed until resolution, stabilization, the event is otherwise explained, or the participant is lost to follow-up (as defined in section 7.3.).
- Follow-up period duration after the last dose administered will be determined based on IMP's half-life and toxicity profile.

8.6.4. Assessment of AEs and SAEs

Complete procedure is described in the trial safety Working Instructions (WI).

Seriousness

For any adverse event, the investigator must determine whether the event meets one or more of the seriousness criteria described in Table 8.3.

Severity (grading)

All AEs and SAEs will be assessed for severity, according to the Division of AIDS (DAIDS) Table for Grading the Severity of Adult and Paediatric Adverse Events, version 2.1 (July 2017), see Appendix 9.

For AEs not included in the DAIDS scale, the following guidelines will be used to describe severity:

Table 8.4 AE severity scale (not included in the DAIDS table)

Grade 1 (Mild)	Mild or transient discomfort, without limitation of normal daily activities; no medical intervention or corrective treatment required.
Grade 2 (Moderate)	Mild to moderate limitation of normal daily activities; minimal medical intervention or corrective treatment required.
Grade 3 (Severe)	Marked limitation of normal daily activities; medical intervention and corrective treatment required, possible hospitalization.
Grade 4 (Life-threatening)	Severe limitation of normal daily activities; medical intervention and corrective treatment required, almost always in a hospital setting.

Causality

The investigator must assess the causality of all AEs/SAEs in relation to IMP, research procedures, and concomitant medications, using the following guidelines:

- **Related** – The AE is known to occur with the study intervention, there is a reasonable possibility that the study intervention caused the AE, or there is a temporal relationship

between the study intervention and event. Reasonable possibility means that there is evidence to suggest a causal relationship between the study intervention and the AE.

- **Not Related** – There is not a reasonable possibility that the administration of the study intervention caused the event, there is no temporal relationship between the study intervention and event onset, or an alternate aetiology has been established.

All AEs/SAEs for which the investigator or the sponsor considers a causal relationship to be a reasonable possibility are considered suspected SARs.

Assessment on expectedness is usually done by the sponsor.

8.6.5. Recording and reporting of AEs and SAEs

- All information on AEs (non-serious and serious) and pregnancies should be recorded on the appropriate eCRF (eCRF completion will be detailed into eCRF user manual).
- Any AE that meets the definition of an SAE or AE of special interest (AESI, see section 8.6.11) must be notified immediately (within 24 hours of site awareness) on the corresponding SAE form.
- In case of eCRF unavailability, investigators should report all SAEs using the paper CRF form, dated and signed, and transmit it to the Sponsor and the delegated designee, Inserm-ANRS Pharmacovigilance Office, by fax or via a secured website for data transfer.

8.6.6. Regulatory reporting requirements for SAEs

- Complete procedure is described in the trial Safety Management Plan (SMP).
- On behalf of the Sponsor, the Trial Safety Group (TSG), including Inserm-ANRS Pharmacovigilance Office staff, the medical officer (or an internal or external medically qualified delegate, mainly clinician) of Oslo University Hospital (OUH) and Clinical Trials Unit (CTU) representative, will review all SAE reports received.
- The role of the TSG will be detailed in the SMP.
- In case of lack of consensus within the TSG regarding the causality of the event, the final decision for the initial reporting to the applicable regulatory authorities will lay with the Inserm-ANRS Pharmacovigilance Office.
- The Inserm-ANRS Pharmacovigilance unit is responsible for assessing the causality and expectedness (using the applicable Reference Safety Information e.g., as given in the IB or SmPC) of all SAE reports received, in relation to the IMP, research procedures and concomitant medication (e.g., drug-drug interactions).
- All Suspected Unexpected Adverse Reactions (SUSARs) must be reported, within the legal timeframe, by the Inserm-ANRS Pharmacovigilance unit to the European

Medicine Agency (EudraVigilance, EMA), the National Competent Authority of the concerned Member State and concerned Ethics Committees according to local requirements.

- Fatal and life-threatening SUSARs must be reported within 7 days, other SUSARs within 15 days. If regulatory timeframes differ from the above timelines in participating countries, then local requirements should take precedence and be adhered to.
- The Inserm-ANRS Pharmacovigilance unit will immediately inform the National Competent Authorities of each member state and concerned Ethics Committees of safety data or safety issues that might alter the current benefit-risk assessment of the trial and may be relevant in terms of participant safety.
- Once a year, the Inserm-ANRS Pharmacovigilance unit will submit to the National Competent Authority and the Ethic Committee of each Member State a Development Safety Update Report (DSUR), according to applicable laws and regulations.

8.6.7. Pregnancy

- Pregnancy during hospitalisation is highly unlikely, and no specific procedures will be undertaken to discover pregnancies during hospitalisation except for the pregnancy test at screening.
- Depending on the IMP safety profile, pregnancy occurrence involving the participant's partner will be also recorded.
- Details of all pregnancies, including outcome, neonate information and any post-study pregnancy-related SAE, will be collected after the start of study intervention and as long as the patient is exposed to drug effects (detailed in the intervention-specific sub-protocol).
- Investigator will record pregnancy information on the appropriate form and submit it to the sponsor and the delegated designee, Inserm-ANRS Pharmacovigilance Office, within 24 hours of learning of the female participant pregnancy.
- While pregnancy itself is not considered to be an AE, any pregnancy complication, abnormal outcome (e.g., spontaneous abortion, foetal death, stillbirth, congenital anomalies, ectopic pregnancy) or elective termination of a pregnancy for medical reasons will be reported with the same timeframe as an SAE.
- Further details are described in the trial Working Instructions.

8.6.8. Cardiovascular and Death Events

The sponsor or sponsor representative should be informed, immediately and without delay (and at the latest within 24 hours of the investigator being aware of the event) that a participant is dead using the corresponding eCRF death form. The cause of death should be recorded by the

investigator in the eCRF if known. In addition to the declaration of death, an SAE declaration should be recorded in the eCRF.

Handling of cardiovascular events will be detailed in the intervention-specific sub-protocol

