3. to determine the effect of therapeutic interventions on biochemical parameters	3. Biochemical parameters including inflammatory markers (C-reactive protein, ferritin, lactate dehydrogenase, procalcitonin, D-dimer, leukocyte subsets and cytokine panels) during hospitalisation
4. to assess the safety impact of therapeutic interventions on major serious adverse events	4. Occurrence of serious adverse events leading to study treatment discontinuation or death
5. to determine the effect of therapeutic interventions on patient reported outcomes	5. The Oslo COVID-19 QLQ-PW80 subscale scores at Day 91

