 - If ferritin and procalcitonin are not routinely gathered at a site for clinical follow-up of the patient, these analyses should be prioritized at baseline, D8 and D15.
- Obtain vital signs including height in cm and weight in kg, see section 8.3.2.
- Collect data on oxygen therapy, see section 8.1.2.
- Register WHO COVID-19 disease progression scale (0-10), see section 8.1.1.
- Details of study treatment administration according to intervention-specific sub-protocol

Assessment until discharge:

Participants will be assessed daily for AE and SAE while hospitalized, see section 8.6.

- Note AE and SAE in the eCRF upon notice
- Safety concerns should be discussed with the sponsor to determine if the participant should continue or discontinue study intervention

The following clinical data will be noted in the eCRF obtained on Days 3, 5, 8 (± 1 day), and thereafter weekly (Day 15 ± 3 , Day 22 ± 3 , Day 29 ± 3 , etc.)

- Obtain vital signs, see section 8.3.2.
- Collect data on oxygen therapy, see section 8.1.2.
- Register WHO COVID-19 disease progression scale (0-10), see section 8.1.1.
- Review concomitant medication and note changes in the eCRF
- Draw and register blood samples for clinical safety laboratory tests (see section 8.3.5.)
 - If ferritin and procalcitonin are not routinely gathered at a site for clinical follow-up of the patient, these analyses should be prioritized at baseline, D8 and D15.

Details of study treatment adherence and administration will be given in the intervention-specific sub-protocol.

For level II of commitment:

Blood samples and naso/oropharyngeal swabs should be obtained at baseline (D1) before drug intervention starts. In addition, blood samples will be obtained on Days 3, 8, 15 and 22 (all ± 1 day), and naso/oropharyngeal swabs on Days 3, 8, 15 (all ± 1 day), as long as the patient is hospitalized.

Day 15 ± 3 , 29 ± 3 , 61 ± 7 :

If the patient has been discharged, the following information is gathered by phone or by reviewing the patient records:

- Alive or dead

If alive, recovery status

- Readmitted to hospital
- If readmitted, date of readmission and reason for readmission. Report as SAE.
- Review concomitant medication
- Adverse events by open-ended and non-leading verbal questioning of the participant

Follow-up assessment at Day 91 ± 14 :

A follow-up assessment by phone will be performed on Day 91 (± 14 days):

- Alive or dead

If alive, recovery status

- Readmitted to hospital

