8.6.9. Disease-related Events (DREs) and/or Disease-related Outcomes not qualifying as AEs or SAEs

These events may refer to disease- or complication-related events that are common in Covid-19 patients and can be serious/life-threatening.

They are reported systematically on the eCRF in the pre-defined daily data sections. However, they will NOT be reported as SAE in the eCRF, even though the event may meet the definition of an SAE, unless the investigator considered that there is a reasonable possibility that the study intervention (blinded investigational agent/placebo or study-supplied SoC treatment) caused the event.

These events may occur during the initial hospitalization, lead to a re-admission, or occur in a later hospitalization during follow-up.

The DREs are given in Section 10.4 Appendix 4.

Some of these events can be recorded as AESI, depending on the IMP profile.

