9.3.5. Safety analyses

Safety endpoints include serious adverse events (SAEs) leading to study treatment discontinuation and death. SAEs will be coded using the current version of the Medical Dictionary for Regulatory Activities (MedDRA). SAEs leading to study treatment discontinuation and death will be summarized with number and proportion. More details on the statistical analysis will be provided in the SAP.

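### The protocol gives conflicting SAE filing rules for fatal disease-related events and for readmissions caused by them, so the size of the fatal part of safety endpoint 4 depends on which section a site follows

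*Protocol*

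**What the plan says.** Two instructions make an event an SAE without exception for its cause.

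- Deaths, Protocol 8.6.8: the death form goes in within 24 hours, and "In addition to the declaration of death, an SAE declaration should be recorded in the eCRF".
- Readmissions, Protocol Section 8 (follow-up at Days 15, 29 and 61, repeated for Day 91): "If readmitted, date of readmission and reason for readmission. Report as SAE".

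Two instructions take a class of events out of SAE reporting.

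- Protocol 8.6.9, on the disease-related events of Appendix 4: "However, they will NOT be reported as SAE in the eCRF, even though the event may meet the definition of an SAE". The one exception is an event that the investigator suspects was due to the trial treatment. The section says that these events may lead to a readmission.
- Protocol 8.6.1 repeats the exemption: "Except disease-related events as defined in section 8.6.9. and exceptions mentioned above, all SAEs will be recorded and reported to the sponsor".

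The endpoint that uses these filings is number 4 in Table 3.1: "Occurrence of serious adverse events leading to study treatment discontinuation or death". Protocol 9.3.5 joins the two parts differently: "Safety endpoints include serious adverse events (SAEs) leading to study treatment discontinuation and death".

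**The concern.** Appendix 4 lists events that can kill a patient with severe COVID-19, among them severe ARDS, cardiac arrest, pulmonary embolism, stroke and ventilator-associated pneumonia. A participant who dies of one of these, with no suspicion of the study intervention, needs an SAE declaration under 8.6.8 and must not have one under a literal reading of 8.6.9. A participant readmitted for one of them meets the same conflict between Section 8 and 8.6.9.

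Endpoint 4 counts SAEs, so it inherits whichever filing rule a site applied. If sites differ, the SAE field is inconsistent before any analysis begins, and an analysis plan cannot restore it from that field alone. At stake are the size and meaning of the fatal part of endpoint 4, and the completeness of the SAE listings and of 24-hour reporting.

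**Working it through.** **Step 1. Rules side by side**

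| Event, judged unrelated to the intervention | 8.6.8 or Section 8 | 8.6.9 and 8.6.1 |
|---|---|---|
| Death from an Appendix 4 event | SAE declaration | not reported as SAE |
| Readmission for an Appendix 4 event | SAE | not reported as SAE |
| Death from an event not on the list | SAE declaration | SAE |
| Any of these, if attributed to the intervention | SAE | SAE |

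The conflict is confined to the first two rows. Nothing in the protocol ranks the sections.

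**Step 2. What reaches endpoint 4**

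The endpoint covers SAEs leading to treatment discontinuation or death. In the only sub-protocol shown (synopsis, 10.8.1), study drug is given for at most 14 days and only in hospital, so a readmission after discharge will rarely lead to discontinuation. The readmission row therefore matters mainly for listings and expedited reporting. The death row bears directly on the endpoint, unless death is meant to count in its own right. The differing conjunctions in Table 3.1 and 9.3.5 leave that open.

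**Step 3. Size of the fatal part**

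The plan states no figure for endpoint 4, so there is none to reproduce. Inputs from 9.5.1 (Part B): 15% deaths on control, 10% on the intervention, 950 per arm. These rates agree with the hazard ratio in Table 9.3: ln(0.90)/ln(0.85) = 0.648.

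Assumptions not in the documents: the share s of deaths that are disease-related, and the fraction f of those attributed to the intervention.

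Events per arm = 950 × death rate × [(1 − s) + s·f]. The risk difference (RD) is intervention minus control, with a Wald 95% interval.

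- Every death an SAE: 950 × 0.10 = 95 and 950 × 0.15 = 142.5, about 237 in all. RD −5.0 points (−8.0 to −2.0).
- s = 1, f = 5% in both arms: 4.8 vs 7.1, about 12 in all. RD −0.25 (−0.96 to +0.46).
- s = 1, f = 10% in both arms: 9.5 vs 14.2, about 24 in all. RD −0.5 (−1.5 to +0.5).
- s = 1, f = 20% in both arms: 19.0 vs 28.5, about 48 in all. RD −1.0 (−2.4 to +0.4).
- s = 0.5, f = 10% in both arms: 52.3 vs 78.4, about 131 in all. RD −2.75 (−5.0 to −0.5).

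**Step 4. Direction**

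With equal f in both arms, RD = −0.05 × [(1 − s) + s·f], which is negative whenever any death counts. The sign changes only if attribution is sufficiently higher on the intervention. With s = 1 it must exceed 1.5 times the control fraction. With no attribution on control, it must exceed 12.5% for s = 0.8 [(1.5 × 0.2 − 0.2)/0.8] and 50% for s = 0.5 [(1.5 × 0.5 − 0.5)/0.5].

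**Step 5. Illustration with non-fatal SAEs added**

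Suppose, purely as an assumption, that non-fatal SAEs leading to discontinuation occur in 2% on control and 5% on the intervention and do not overlap with deaths. z is the difference over its unpooled standard error.

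- No deaths counted: 5.0% vs 2.0%, z = +3.57.
- 10% of deaths counted in each arm: 6.0% vs 3.5%, z = +2.57.
- All deaths counted: 15.0% vs 17.0%, z = −1.19.

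Counting all deaths hides the assumed excess. The last figure is not significant at the two-sided 5% level, and the pattern comes from the assumed 3-point excess, not from anything in the protocol.

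**The case against.** The best counter-argument is that deaths are not truly in conflict. Death is absent from Appendix 4, 8.6.9 speaks of serious or life-threatening events without mentioning fatal ones, and 8.6.8 is the section written for deaths. Read as the specific rule, it would mean that a disease-related event alone is not an SAE but a death always gets a declaration. That is reasonable and may be what was intended. It is not stated, however, and 8.6.9 exempts events even when they meet the SAE definition, whose first criterion in Table 8.3 is death.

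A reader might go further and infer that the two rules could make the same data show harm under one and benefit under the other. The documents do not support that. With equal attribution the fatal part keeps its sign. Unequal attribution is conceivable in the open-label comparisons that 6.3 allows, but less so in the double-blind baricitinib trial, and the attribution clause covers placebo and study-supplied standard of care too. Masking of a non-fatal excess needs the invented rates of Step 5, and even there the far end is no detectable difference.

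Nor does it follow that the data monitoring committee would be misled. Every death is on the death form with its cause if known, disease-related events are recorded elsewhere in the eCRF, and death is the Part B primary endpoint. The exceptions under Table 8.3 also narrow which readmissions need immediate reporting. Finally, the safety SOP, Working Instructions and Safety Management Plan are not shown and may clarify practice, but they would not remove the contradiction from the protocol.

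**Conclusion.** The contradiction is real and unresolved in the protocol. For readmissions it is direct, because 8.6.9 names them; its consequence is mostly for SAE listings and expedited reporting. For deaths a reconciling reading exists but is unstated, and the choice changes the fatal part of endpoint 4 from about 237 events to about 12 to 48. That lower range assumes that all deaths are disease-related and that 5% to 20% are attributed equally in both arms. With a smaller disease-related share the gap narrows (about 131 events at 50% disease-related and 10% attributed).

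The calculation borrows the 60-day mortality rates as a stand-in, since endpoint 4 has no stated window and SAE collection continues to the Day 91 follow-up. The finding is one of inconsistent filing and an ambiguous count, not of a reversed safety conclusion. It should be corrected.

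**What to change.** 1. Reconcile 8.6.1, 8.6.8, 8.6.9 and the follow-up instructions in Section 8, so that one stated rule covers fatal disease-related events and readmissions for disease-related events. Which rule to adopt is for the sponsor; it needs to be the same in all four places.
2. For endpoint 4, take deaths from the eCRF death form for all participants, whatever the cause or attribution.
3. Report death and SAE leading to treatment discontinuation as separate lines by arm, so that neither can obscure the other.
4. Use the same conjunction in Table 3.1 and 9.3.5, and make clear whether death counts in its own right.

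The cost is a wording amendment and an instruction on the SAE and death forms. The death form already exists, so no new data are needed.
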